390 groups will be regularly examined by the DMSC to identify any bias in the commencement of resuscitation attempts.

391

392 **Patient Exclusion criteria**

393

- 394 • Patient detained by Her Majesty's Prison Service
- 395 • Previously recruited to the trial (determined retrospectively)
- 396 • Resuscitation considered inappropriate (see below)
- 397 • Advanced airway management inserted by another HCPC registered paramedic, doctor or nurse already in
398 place when AIRWAYS-2 paramedic arrives at patient's side (when the first paramedic to arrive is not
399 participating in AIRWAYS-2)
- 400 • Known to already be enrolled in another pre-hospital randomised trial
- 401 • Mouth opening <2 cm

402

403 This last exclusion has been applied because SADs are not designed for use in patients with significantly reduced
404 mouth opening. There is a risk of post-randomisation bias being introduced by this exclusion criteria, but in our
405 feasibility study only 2/711 patients (0.3%) were excluded on these grounds. We will monitor this exclusion, under the
406 guidance of the DMSC, and should the exclusion rate exceed 1% we will take action to address this through enhanced
407 training and supervision.

408

409 Standardised guidelines, based on those produced by JRCALC, will be applied to determine patients for whom a
410 resuscitation attempt is inappropriate. This is the case when there is no chance of survival, the resuscitation attempt
411 would be futile and distressing for relatives, friends and healthcare personnel and where time and resources would be
412 wasted undertaking such measures. When any one or more of the following conditions exist, resuscitation and
413 enrolment in the trial will not take place.

414

- 415 1. massive cranial and cerebral destruction
- 416 2. hemicorporectomy
- 417 3. massive truncal injury incompatible with life (including decapitation)
- 418 4. decomposition/putrefaction
- 419 5. incineration
- 420 6. hypostasis
- 421 7. rigor mortis
- 422 8. A valid do not attempt resuscitation order or an Advanced Directive (Living Will) that states the wish of the
423 patient not to undergo attempted resuscitation
- 424 9. When the patient's death is expected due to terminal illness
- 425 10. Efforts would be futile, as defined by the combination of **all three** of the following being present
- 426 (a) More than 15 minutes since the onset of collapse
- 427 (b) no bystander CPR prior to arrival of the ambulance

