878 of patients discharged from hospital consented to follow up at 3 months. We would expect similar figures for this
879 study.

880

881 **5.13 Expenses**

882

883 A payment of overtime and travel expenses will be made to paramedics each time they attend one of the study training
884 sessions. The initial training session is mandatory for all paramedics who wish to take part in the study and attendance
885 at the refresher training and exit training will be strongly encouraged.

886

887 No expenses will be payable to participants because participants will not be required to make any additional visit to
888 hospital, to their GP or to any other health or welfare professional for the study.

889

890

891 **6. STATISTICAL ANALYSES**

892

893 **6.1 Plan of analysis**

894

895 The primary outcome of mRS at discharge or 30 days post OHCA (presented dichotomously as good recovery (0-3) or
896 poor recovery/death (4-6)), and other binary outcomes, will be analysed using a multilevel logistic regression model, in
897 which the data are nested within attending paramedic. Repeated mRS scores will be analysed using multilevel logistic
898 regression for repeated measures. Survival to 6 months and other time-to-event outcomes will be analysed using

AIRWAYS-2

21st December 2017

Protocol – version 6.0.

899 survival analysis methods, again allowing for clustering of patients by paramedic. Patient responses to the individual
900 EQ-5D questions will simply be described because these will be available only for survivors. Overall quality of life
901 utility scores and patient survival will be analysed jointly to assess whether the use of the i-gel supraglottic airway
902 device simultaneously improves the patient's quality of life and reduces the risk of death.

903

904 Enrolled patients who are subsequently identified as being ineligible will remain within the trial and be included in
905 analyses with the exception of a) patients who were subsequently found to have been previously enrolled in the trial; b)
906 patients who were inadvertently enrolled in the study due to being treated as a study participant by a paramedic who
907 arrives later than second at the patient's side; c) patients who are subsequently identified as being children (aged < 16
908 years); individuals aged 16 and 17 years will be included in analyses." . Analyses will be done according to the
909 principle of intention-to-treat, and reported according to the CONSORT guidelines [46, 47].

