1712 commenced or continued by ambulance staff or responder. For specific inclusion/exclusion criteria and details
1713 of study patients and paramedics see template **Figures F1** and **F2**. 'Trial patients' are those who are
1714 resuscitated, attended by an A2 paramedic and meet the eligibility criteria.

1715 Recruitment over time against targets will be presented by trust and overall (**Figures F3, F4 and F5**).

1716 In the context of this trial, 'advanced airway management' refers to the use of intubation, the i-gel device or
1717 other supraglottic airway devices.

1718 **3.1 Consent**

1719 Due to the emergency nature of the trial, we have ethical approval to enrol patients without consent and seek
1720 consent for further participation from patients who survive to discharge from intensive care (ICU). We have
1721 approval to retain data collected up to the point of approach (or death if this occurs before approach) as well
1722 as mRS at hospital discharge or death for all patients regardless of whether they consent.

1723 Patients may choose one of the following three options when presented with the trial information and consent
1724 form:

1725 Active follow-up - Routine data will be utilised and the patient will be actively followed up at hospital
1726 discharge, and 3 and 6 months after the index OHCA. Quality of life and mRS will be collected at these three
1727 time points.

1728 Passive follow-up - Only routine data will be collected and the patient will not be contacted again about the
1729 study.

1730 Does not wish to participate – No further data collection will take place.

1731 **3.2 Flow of participants**

1732 Participant and paramedic flow will be described via flowcharts (see **Figures F1** and **F2**). Follow-up will
1733 occur at three and six months post OHCA (target ± 4 weeks) for patients who consent to active follow-up.

1734 **3.3 Characteristics of non-study patients**

1735 All resuscitated patients who are attended by an A2 paramedic and meet the eligibility criteria are
1736 automatically enrolled in the study and classed as trial patients. Key demography and initial cardiac arrest
1737 details are collected for all resuscitated patients, including those who are not attended by an A2 paramedic or
1738 are ineligible; these details will be described for trial and non-trial patients (**Table T1**). Resuscitated non-trial
1739 patients are referred to as population 0 in this document.

1740 **3.4 Randomisation**

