1741 Paramedics are randomised (1:1 allocation) to either the i-gel or intubation group using an in-house internet-
1742 based system. Randomisation is stratified by ambulance trust, clinical experience (greater than or equal to 5
1743 years full-time operational experience verses less than 5 years full-time operational experience) and the
1744 location of the paramedic's base ambulance station (greater than or equal to 5 miles verses less than 5 miles
1745 from the nearest hospital with an emergency department that receives cardiac arrest patients; this is a proxy
1746 for urban vs. rural location).

1747 To avoid bias that may be introduced by the cluster randomisation all patients who are resuscitated, attended
1748 by an A2 paramedic and meet the eligibility criteria are automatically enrolled in the trial and considered trial
1749 patients. If the attending paramedic forgets to treat a patient according to the A2 protocol or chooses not to
1750 follow the protocol, the patient is still enrolled in the trial and the attending A2 paramedic is still considered
1751 to be the enrolling paramedic and will be asked to complete a CRF; these patients are noted on the database as
1752 not 'consciously' enrolled and if they did not treat the patient according to their allocation will be counted as a
1753 protocol deviation (see section 3.5).

1754 **3.5 Protocol deviations**

1755 The following protocol deviations will be considered:

- 1756 • A patient did not meet the study eligibility criteria but was consciously enrolled in the study by the
1757 attending A2 paramedic. This may occur because the paramedic believed the patient to be eligible at the
1758 time of treatment but later found out they were not. These patients are not considered to be ‘trial patients’
1759 and will not be included in the study population, but such deviations will be noted.
- 1760 • The wrong paramedic enrolled the patient. According to the A2 protocol, if a patient is eligible the first
1761 A2 paramedic on scene should enrol and treat the patient. Sometimes, due to reasons such as
1762 miscommunication, a second A2 paramedic may enrol and treat the patient instead. These patients will be
1763 analysed in the allocated intervention group of the *first* A2 paramedic on scene.
- 1764 • The enrolling A2 paramedic did not perform any advanced airway management but another paramedic

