- **Population 0:** The population of patients who were resuscitated but did not become trial patients (either because they were not attended by an A2 paramedic or were ineligible). Characteristics of this population will be compared to those in population 1 (see **Table 1**).

1821 The primary analysis will be performed on an ITT basis, with patients grouped by the allocation of their first
1822 A2 paramedic on scene (see section 6.2.2 for details).

1823 **3.8 Safety population**

1824 The safety population is all trial patients (cf. analysis population for the primary outcome). Only serious
1825 adverse events which are unexpected and related to the intervention are collected, so numbers are expected to
1826 be low. These will be presented along with all intervention details.

1827

1828 **4. DATA SOURCES**

1829 A number of variables collected in AIRWAY-2 are recorded in more than one place. The following table details
 1830 these variables and identifies the primary data sources and the order in which data will be selected; for example
 1831 gender will be taken from Form G2, if not available from Form G2 then Form G will be used, if not available
 1832 from Form G then Form E1 will be used and if not available from Form E1 then Form B will be used.

Variable	Data sources	Order of preference
Date and time of incident	Form A (CAD) Form E1 (paramedic)	Always use form A as this should be available for all patients
Gender	Form B (minimal dataset/CAD) Form E1 (paramedic) Form G (hospital details, only available for those surviving to hospital admission)	1. Form G2 2. Form G 3. Form E1 4. Form B
Date of birth (DOB)	Form B (minimal dataset/CAD) Form E1 (paramedic) Form G (hospital details, only available for those surviving to hospital admission)	1. Form G2 2. Form G 3. Form E1 4. Form B
Approximate age (Note. This variable will only be used if the date of birth is missing from all sources. If date of birth is recorded, age will be derived (see Section 5))	For patients who do not survive to hospital, age may be estimated on scene. If this is the case, this will be recorded on Form B (minimal dataset/CAD) Form E1 (paramedic)	1. Form E1 2. Form B
Presenting rhythm	Form B (minimal dataset/CAD) Form E1 (paramedic)	1. Form E1 2. Form B
Was event witnessed?	Form B (minimal dataset/CAD) Form E1 (paramedic)	1. Form E1 2. Form B
Who was the event witnessed by?	Form B (minimal dataset/CAD) Form E1 (paramedic)	1. Form E1 2. Form B

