1860 higher scores denoting higher Quality of Life (QoL)).

1861 Trial patients who did not survive to 30 days/hospital discharge will be assigned EQ-5D visual analogue scale
1862 and summary index scores of zero.

1863

1864 **5.4 Other variables**

New variable	Rules
POPULATION 0 and 1:	
Age	If date of birth ≠ missing: Age= (OHCA date – Date of birth) /365.25 If date of birth = missing: Age= approximate age (see section 4) Else missing
999 call to first crew arrival time (mins)	(First crew arrival date-incident date)*24*60 + (First crew arrival time-incident time)
POPULATION 1:	
Trial patient	If was resuscitation attempted=Yes and was incident attended by AIRWAYS-2 paramedic=Yes and did patient meet eligibility criteria=Yes, then = Yes

New variable	Rules
Survival status to hospital discharge	
If was resuscitation attempted=No or was incident attended by AIRWAYS-2 paramedic=No or did patient meet eligibility criteria=No, then = No
 
Else missing
 
If admitted to ED (Form D)=No, then = Died on scene
 
If admitted to ED=Yes, and survived to ICU admission (Form G)=No, then = Died prior to ICU admission
 
If admitted to ED=Yes, and survived to ICU admission=Yes, and survived to ICU discharge (Form G)=No, then = Died prior to ICU discharge
 
If admitted to ED=Yes, and survived to ICU admission=Yes, and survived to ICU discharge (Form G)=Yes, and transferred=Yes and level of care in transferred hospital (form G2)=Level 3 and survived to ICU discharge (Form G2)= No, then = Died prior to ICU discharge
 
If admitted to ED=Yes, and survived to ICU admission=Yes, and survived to ICU discharge=Yes and ((transferred = No) or (transferred=Yes and level of care admitted to is level 2 or 1) or (transferred=Yes and level of care admitted to is level 3 and survived to ICU discharge=Yes)) and (mRS (Form H2/I2)=6 or (mRS (Form H2/I2) ≠6 & has patient died since ICU discharge (but prior to hospital discharge) (Form W2) = Yes) or survived to hospital discharge (form H3/I3)=No), then = Died prior to hospital discharge
 
If admitted to ED=Yes, and survived to ICU admission=Yes, and survived to ICU discharge=Yes and ((transferred = No) or (transferred=Yes and level of care admitted to is level 2 or 1) or (transferred=Yes and level of care admitted to is level 3 and survived to ICU discharge=Yes)) and (mRS≠6 or survived to hospital discharge=Yes, then = Survived to 30 days/hospital discharge)

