Utstein comparator group	if event witnessed by = bystander and presenting rhythm = VF or pulseless VT, then = Yes if (event witnessed by = bystander and presenting rhythm = Asystole OR PEA OR unknown) or event witnessed by = EMS, then = No Else missing
Protocol deviation 1: consciously enrolled but ineligible	if consciously enrolled = Yes AND trial patient = No, then = Yes if trial patient = Yes, then = No Else missing
Protocol deviation 2: wrong paramedic enrolling patient	if Paramedic AIRWAYS-2 ID (Form A) ≠ Paramedic AIRWAYS-2 ID (Form E1) and Paramedic AIRWAYS-2 ID (Form E1) ≠ missing and trial patient = Yes, then = Yes if Paramedic AIRWAYS-2 ID (Form A) = Paramedic AIRWAYS-2 ID (Form E1) and Paramedic AIRWAYS-2 ID (Form E1) ≠ missing and trial patient = Yes, then = No
Protocol deviation 2: wrong paramedic enrolling patient resulting in allocation crossover	if protocol deviation 2 = Yes and allocation of enrolling paramedic ≠ allocation of first A2 paramedic on scene, then = Yes if protocol deviation 2 = Yes and allocation of enrolling paramedic = allocation of first A2 paramedic on scene, then = No Else missing
Protocol deviation 3:	if 'If no [airways management attempt completed on CRF E2], why?' = Further airway management commenced once A2 paramedic arrived but not carried out by enrolling A2 paramedic and trial patient = Yes, then = Yes

New variable	Rules
	if 'has at least one airway management attempt recorded on CRF E2?' ≠ missing and 'If no [airways management attempt completed on CRF E2], why?' ≠ Further airway management commenced once A2 paramedic arrived but not carried out by enrolling A2 paramedic and trial patient = Yes, then = No Else missing
Protocol deviation 4	if (Paramedic allocated to i-gel and first advanced airways management attempt is intubation or other SGA) or (Paramedic allocated to intubation and first advanced airways management attempt is i-gel or other SGA and paramedic is not a solo responder), then = Yes if first advanced airway management attempt matches paramedic allocation, then = No Else missing (including patients with no advanced airways management attempts)

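### The SAP limits the safety population to patients confirmed eligible, so a patient given a study airway and later found ineligible leaves the safety denominators, contrary to Protocol 6.1

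*Protocol*

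**What the plan says.** SAP 3.8 takes over the primary-outcome population for safety: "The safety population is all trial patients (cf. analysis population for the primary outcome". Who counts as a trial patient is settled in three places:

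- SAP 3 describes trial patients as those who are "resuscitated, attended by an A2 paramedic and meet the eligibility criteria".
- The derivation in SAP 5.4 gives a negative result on eligibility alone: "did patient meet eligibility criteria=No, then = No".
- SAP 3.5 deals with the patient whom the paramedic took to be eligible when treating and who turned out not to be. Such patients are not trial patients "and will not be included in the study population, but such deviations will be noted". SAP 5.4 derives them as protocol deviation 1: "if consciously enrolled = Yes AND trial patient = No, then = Yes".

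Protocol 6.1 has a different rule: "Enrolled patients who are subsequently identified as being ineligible will remain within the trial and be included in" the analyses. It then names three exceptions: patients already enrolled once, "patients who were inadvertently enrolled in the study due to being treated as a study participant by a paramedic who" arrived later than second, and children under 16. Patients aged 16 or 17 stay in.

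Three other places bear on the point. Protocol 8.4 starts adverse event recording when the intervention starts. SAP 6.3 and 3.8 restrict safety data to unexpected serious events related to the intervention and expect few. The T9 skeleton has two columns, for patients who received intubation first and patients who received the i-gel first.

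**The concern.** Eligibility decides who should inform the efficacy comparison. It does not change whether a patient was exposed to a device because of the trial. SAP 3.8 nevertheless uses an eligibility filter, applied after treatment, to define safety. A serious device-related event in a wrongly enrolled patient would have no place in the analysed safety population, and the patient would be missing from the denominator whether or not an event occurred.

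The SAP also departs from Protocol 6.1 without saying so. Two analysts, one working from each document, would produce different safety denominators. Because few events are expected, whether a single case belongs in the table should not depend on which document is followed.

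**Working it through.** The point turns on definitions, so the passages are followed through in order.

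**1. One patient through the SAP.** An AIRWAYS-2 paramedic believes a patient eligible, enrols the patient consciously and attempts the allocated airway. The patient later proves ineligible.
- SAP 5.4: trial patient = No; protocol deviation 1 = Yes.
- SAP 3.5: not in the study population; the deviation is noted.
- SAP 3.7: the patient falls into Population 0 (resuscitated but not a trial patient), for which only characteristics are described.
- SAP 3.8: not in the safety population, so not in the T9 denominator.

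SAP 3.5 sends deviation counts to Table T2 and Figure F6. The T2 skeleton has no row for deviation 1, and both of its row headings are limited to trial patients. Figure F6 is not reproduced, so a count may appear there. No table that can be read gives these patients' safety outcomes.

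**2. The same patient through Protocol 6.1.** The patient stays in the analyses unless one of the three exceptions applies.

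| Reason found ineligible | SAP 3.5 and 3.8 | Protocol 6.1 |
|---|---|---|
| Mouth opening under 2 cm | out | in |
| Prisoner, or in another pre-hospital trial | out | in |
| Aged 16 or 17 | out, if judged ineligible | in |
| Previously enrolled | out | out |
| Paramedic later than second | out | out |
| Under 16 | out | out |

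Restoring Protocol 6.1 repairs the upper three rows. The lower three remain out of safety, although such patients may also have had a study airway attempted.

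**3. Population against table.** T9 is grouped by the device received first. A trial patient who received no advanced airway is in the safety population but has no column in T9. An ineligible patient who did receive one has a natural column but is not in the population. The two do not match in either direction.

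**4. Scale.** The documents give no number of treated but ineligible patients, so the size cannot be calculated. The only related figure is in Protocol 4.4.2: 2 of 711 feasibility patients excluded for mouth opening.
- 2/711 = 0.28%, agreeing with the stated 0.3%. The exact 95% interval is 0.03% to 1.01%.
- The planned total reproduces: 4,400 × (1 + (7.2 − 1) × 0.005) = 4,536 per group, with 7.2 = 2 × 3.6 patients per paramedic. The protocol states 4,535, or 9,070 in total.
- 9,070 × 2/711 ≈ 26, with limits of about 3 and 92. At the protocol's 1% action threshold, 9,070 × 0.01 ≈ 91.

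These would be patients excluded on one criterion, assuming the feasibility rate carries over. They do not count patients in whom a device was tried.

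**The case against.** The strongest reply is that little is lost. Adverse event recording is not tied to confirmed eligibility, and Protocol 8 has events reported under GCP and the sponsor's policy whatever the SAP populations are. SAP 6.3 promises to detail all such events and plans no formal comparison. This largely stands: an event could well appear in a listing. But SAP 6.3 names no population wider than that of 3.8, so inclusion is at best unclear, and the denominator is wrong either way. Regurgitation, aspiration and loss of the airway are analysed as secondary outcomes, but in Population 2, which is also restricted to trial patients, so that route does not catch these patients.

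A second reply is that the defect is mainly the conflict between SAP 3.5 and Protocol 6.1. That is fair for most of the group, but not for the three exceptions. Even there the gap is narrow: a repeat patient's first enrolment remains in the population, and only the later exposure is lost.

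A reader might go further and infer that the rule removes exactly the patients least suited to the device, since Protocol 4.4.2 says of mouth opening: "This last exclusion has been applied because SADs are not designed for use in patients with significantly reduced" mouth opening. The documents do not support that as the main point. It rests on one criterion. The feasibility patients concerned were excluded, and nothing shows that such patients had a device placed. Protocol 6.1 would return any who did. Being a prisoner, previously recruited or in another trial says nothing about suitability for the device.

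**Conclusion.** The point holds. Followed as written, the SAP removes from the safety population, and from the T9 denominators, patients exposed to a study airway through the trial. In doing so it contradicts Protocol 6.1, and it does not fit the exposure basis of T9 or of adverse event recording.

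The size is unknown and probably small. It would be tempting to apply an assumed percentage of ineligible patients to 9,070, but no document gives such a rate, and conscious enrolment is not the same as exposure. Nor do the documents support saying that the safety conclusion would change: safety is descriptive, and events may be listed individually. The verdict assumes only that at least some patients are treated before being found ineligible, which SAP 3.5 itself foresees. It is worth correcting because the remedy is cheap and the present wording leaves the safety denominator in dispute.

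**What to change.** Reconcile SAP 3.5 and 3.8 with Protocol 6.1, stating which rule governs patients later found ineligible. Then replace the sentence in SAP 3.8 along these lines: the safety population is every patient in whom an AIRWAYS-2 paramedic attempted a study airway (i-gel or intubation) as part of the trial, whatever the patient's later eligibility, grouped by device received first. Flag ineligible patients in T9 and T10. Keep the efficacy populations as a separate decision.

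The definition should rest on an attempted airway, not on conscious enrolment, which could add patients in whom no device was tried. The deviation 1 flag finds the candidates, and the airway attempts recorded on Form E2 would identify those exposed.

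The cost is a short SAP amendment and a flag in two outputs, with two drawbacks. The safety denominator will no longer equal the primary-outcome denominator; in particular, trial patients with no study airway attempt by an AIRWAYS-2 paramedic would leave it. Data may also be thinner for ineligible patients, since SAP 3.3 promises only key demography and initial arrest details for resuscitated non-trial patients. A footnote to T9 should state how complete their airway and follow-up data are.

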Time to death event/censor variable	
If (survival status≠survived to 30 days/hospital discharge & survival status≠missing) or has patient died since hospital discharge=Yes, then = 0
 
If survival status=survived to 30 days/hospital discharge & (has patient died since hospital discharge=No or missing), then = 1
 
Else missing
 
Note – if time to death exceeds 183 days, then it will be censored at 183 days

72 hour survival	
if time to death≥72 hours, then = Yes
 
if time to death<72 hours & time to death censor variable=0, then = No
 
if time to death<72 hours & time to death censor variable=1 & (mRS date-incident date) >3 & mRS at 30 days/discharge≠6, then = Yes
 
Else missing

Time to death: 0 to 72h	
if time to death≥72 hours, then = 72h
 
if time to death<72 hours & time to death censor variable=0 (patient died), then = time to death

New variable	Rules
	if time to death < 72 hours & time to death censor variable = 1 (censored) & ((30 day/discharge mRS date - incident date) > 3 & mRS at 30 days/discharge ≠ 6), then = 72h
	if time to death < 72 hours & time to death censor variable = 1 (censored) & ((30 day/discharge mRS date - incident date) ≤ 3 & mRS at 30 days/discharge ≠ 6), then = time to death
	Else missing
Time to death event/censor variable: 0 to 72h	if time to death ≥ 72 hours, then = 1 if time to death < 72 hours & time to death censor variable = 0 (patient died), then = 0 if time to death < 72 hours & time to death censor variable = 1 (censored), then = 1 Else missing
First crew arrival to first A2 paramedic arrival (mins)	(First A2 arrival date - First crew arrival date) * 24 * 60 + (First A2 arrival time - First crew arrival time)
Time of 999 call to first A2 paramedic arrival (mins)	(First A2 arrival date - Incident date) * 24 * 60 + (First A2 arrival time - Incident time)
Time between incident and discharge/30 day mRS measurement (days)	(mRS date - incident date) if measured face-to-face Else missing
Event witnessed by	if event witnessed by = non-ambulance staff (Form E1) or (event witnessed by = missing (Form E1) and event witnessed by = bystander (Form B)), then = bystander If event witnessed by = AIRWAYS-2 paramedic or ambulance staff (Form E1) or (event witnessed by = missing (Form E1) and event witnessed by = EMS (Form B)), then = EMS Else missing

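### SAP 5.4: the last two branches of the survival-status rule overlap with no stated order, and the survivor branch accepts a missing mRS, so an unknown outcome is labelled as survival

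*Protocol*

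**What the plan says.** In the SAP, section 5.4 (Other variables), the row for survival status to hospital discharge works through the stages of care. The last two branches apply to patients who left ICU alive.

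- **Ward-death branch.** It is met if mRS is 6, or if "mRS (Form H2/I2) ≠6 & has patient died since ICU discharge (but prior to hospital discharge) (Form W2) = Yes", or if "survived to hospital discharge (form H3/I3)=No), then = Died prior to hospital discharge".
- **Survivor branch.** It is met if "mRS≠6 or survived to hospital discharge=Yes, then = Survived to 30 days/hospital discharge".

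The row has no closing line for records that fit nothing. The neighbouring rows for trial patient and date of death do have one. Elsewhere in 5.4 blanks are excluded in so many words, for example "Paramedic AIRWAYS-2 ID (Form E1) ≠ missing" in protocol deviation 2.

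The time-to-death event/censor variable then uses the result. Deaths are coded by "If (survival status≠survived to 30 days/hospital discharge & survival status≠missing) or has patient died since hospital discharge=Yes, then = 0", and censored patients by "If survival status=survived to 30 days/hospital discharge & (has patient died since hospital discharge=No or missing), then = 1". The first of these tests whether survival status is missing, so the authors expected that value to occur.

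**The concern.** Two things go wrong when the branches are applied as printed.

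First, a blank mRS is not equal to 6, so it satisfies the survivor branch by itself. A patient about whom nothing is known after ICU discharge is therefore labelled as having survived.

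Second, the two branches are not exclusive. The survivor branch does not look at W2 at all, and it does not exclude H3/I3 = No. A recorded ward death with mRS 0-5 or missing qualifies for both labels, and the SAP does not say which one stands. If later lines overwrite earlier ones, that patient loses the date of death and is coded as censored. With active or passive consent, the patient is also coded as discharged alive in the hospital-stay variables.

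The second problem does not need missing data. Under SAP 5.1, a patient still in hospital at 30 days is scored then. If that patient scores 0-5 and later dies on the ward, both branches are met. The row is named for survival to discharge, but the survivor label covers 30 days or discharge, so the intended answer is not clear.

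**Working it through.** The plan gives no figure to reproduce; this is a check of logic. The inputs, all from the row in SAP 5.4, are mRS (0-5, 6, missing), ward death on W2 (Yes, or No/missing) and survived to discharge on H3/I3 (Yes, No, missing). That makes 3 × 2 × 3 = 18 patterns for a patient discharged alive from ICU.

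The two conditions are:

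- Died: mRS = 6, or (mRS ≠ 6 and W2 = Yes), or H3/I3 = No.
- Survived: mRS ≠ 6, or H3/I3 = Yes.

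**Literal reading (a blank mRS satisfies mRS ≠ 6)**

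| mRS | Both branches | Died only | Survived only | Neither |
|---|---|---|---|---|
| 0-5 | 4 | 0 | 2 | 0 |
| missing | 4 | 0 | 2 | 0 |
| 6 | 2 | 4 | 0 | 0 |
| Total | 10 | 4 | 4 | 0 |

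- For mRS 0-5 or missing, the four overlaps are W2 = Yes with any H3/I3 value (3) and W2 not Yes with H3/I3 = No (1).
- For mRS 6, the two overlaps are the records with H3/I3 = Yes. These are contradictory records.
- No pattern meets neither branch, so no patient reaching this point can be given a missing status.
- The pattern mRS missing, W2 not Yes and H3/I3 missing meets the survivor branch only.
- Patterns with a recorded death (mRS 6, W2 = Yes or H3/I3 = No) number 4 + 10 = 14. All 14 meet the death branch, 10 of them also meet the survivor branch, and none meets the survivor branch alone.

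**Alternative reading (a blank mRS fails mRS ≠ 6)**

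- The overlaps fall to 4 (mRS 0-5) + 2 (mRS 6) = 6 of 18.
- The fully unknown record now meets neither branch, as one would want.
- However, the W2 clause of the death branch uses the same expression. A patient with a W2 ward death, blank mRS and blank H3/I3 then also meets neither branch and is unclassified. The date-of-death row takes ward deaths from W2 when there is no active or passive consent, so this is a record type the SAP itself foresees.

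Neither reading gives a correct code for every pattern.

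**Where the result goes.** Survival status is reported in Table T6 and drives the rows for date of death, time to death, event/censor, and duration of hospital stay with its event flag. The primary outcome (SAP 5.1) is dichotomised from mRS itself and does not take a good recovery from this variable.

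**The case against.** The best defence is that the list is meant as a sequential chain. Many rules in 5.4 end with a line for everything else, which suggests that the first match wins. The death branch also spells out the case of an mRS other than 6 with a W2 death just before the survivor line. On that reading every recorded ward death is coded as a death. This is probably what was intended, and it stands against the stronger claim a reader might infer, namely that recorded ward deaths are counted as alive. The text does not make that happen: each such death also meets the earlier branch and is lost only if later lines overwrite it. But the order is not stated, and first-match-wins does nothing for the patient with no outcome on any form.

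A second defence is that few patients can be affected. SAP 3.1 reports approval to retain mRS at discharge or death whether or not the patient consents, and protocol 4.6.1 expects almost complete ascertainment. This stands. Blanks are still foreseeable, because the footnotes to Figure F6 reserve a count for missing mRS.

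A third defence is that the consequences are limited, and much of it holds. Non-consenting survivors are censored at ICU discharge, when they were known to be alive, so an unknown later outcome does little harm to the survival-time analysis. The survivor branch of the hospital-stay variable requires active or passive consent. The 72-hour variable asks for an mRS date more than 3 days after the incident when censoring falls before 72 hours. Survival to discharge is not a listed outcome, and SAP 6.1 rules out tests on data not listed as outcomes. A reader might infer that a spurious survival difference between arms would follow; the documents do not support that.

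**Conclusion.** The rule is wrong as written, but the point is minor. Read literally, it labels an unknown post-ICU outcome as survival, and it gives two contradictory labels in 10 of 18 input patterns without saying which prevails. The effect is confined to the survival-status rows of Table T6, the date of death, the time-to-death censor variable and, for consenters, the hospital-stay variables. The conclusion assumes that a blank counts as different from 6, as the text implies by not excluding it. The alternative assumption leaves 6 overlaps and one foreseeable death pattern unclassified.

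The pattern counts do not say how many patients are involved, and several patterns are contradictory records that should be rare. A reader might size the problem from non-consent: 9% of 9,070 is about 816 survivors, and 100% − 86% = 14% of these is about 114. That does not work. The 86% in protocol 5.12 is consent to 3-month follow-up in the feasibility study, and discharge mRS does not depend on consent. The number affected cannot be computed from the documents.

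**What to change.** Reword the one derivation and match the rows that depend on it:

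1. State that the death branch takes precedence, and write it as mRS = 6, or W2 ward death = Yes, or H3/I3 survived = No. Dropping the redundant mRS ≠ 6 term means that a blank mRS cannot defeat it.
2. Assign survived only if (mRS is 0-5 or survived to hospital discharge = Yes) and no death before the stated endpoint is recorded on H3/I3 or W2.
3. Say whether the endpoint is discharge, or discharge or 30 days, so that a death in hospital after a 30-day mRS is clearly counted as died or as survived. Restrict the deaths in steps 1 and 2 to that endpoint.
4. Set all remaining records to unknown/missing and report their number by arm in the Table T6 footnote.
5. Adjust the time-to-death and event/censor rows so that these patients stay in the analysis, censored at the last date known alive, for example ICU discharge. Without this step they would drop out, because both rows now depend on a non-missing survival status.

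With discharge as the endpoint, the 18 patterns then resolve to 14 died, 3 survived and 1 unknown, with no overlap. The cost is a short SAP amendment and a change to the code. No new data are needed.
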